## 10 STATISTICAL CONSIDERATIONS

### 10.1 STATISTICAL ANALYSIS PLAN

The following sections describe the statistical analysis as it is foreseen when the study is being planned. A detailed Statistical Analysis Plan (SAP) will be finalised and approved prior to database lock and will provide details of all analyses to be performed as well as the format of listings and tables to be provided for completion of the Clinical Study Report (CSR). Any deviations from the SAP will be described and justified in the final CSR.

For the safety primary endpoint, we hypothesise that inoculation with ~2 800 viable *P. falciparum* 3D7 parasites infected RBCs and treating with OZ439 and PQP on trial Day 8 will be safe and will result in no SAEs, and will not cause severe malaria symptoms.

This study is not powered to compare IMP doses, but rather to answer the primary objectives.

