^d Serum β -hCG pregnancy test (all female subjects) and follicle stimulating hormone test (FSH) (post-menopausal females) at screening. Urine β -hCG pregnancy test for WOCBP at other indicated time points (Day 0 pre-malaria inoculation, Day 8 pre-OZ439 and PQP administration, EOS).

^e If required, at the Investigator's discretion.

^f May be performed at the Investigator's discretion.

^g Cannulate subjects with an indwelling intravenous cannula for the malaria inoculum, and record which arm is utilised. Cannulate subjects with an indwelling intravenous cannula for the malaria inoculum, and record which arm is utilised. Administer the malaria inoculum of ~2 800 viable *P. falciparum* 3D7 infected human RBCs intravenously in the morning (approximately 9:00 AM). Observe for a minimum of 60 minutes after inoculation to evaluate for immediate adverse reactions. Educate subjects on signs and symptoms of malaria (Appendix 3 of protocol). Emphasise to subjects the importance of returning on the nominated day (approximately Day 8), or as advised by the clinical unit staff, for IP antimalarial treatment. Provide subjects with diary cards and thermometers to record any temperature readings during the study in the event of symptoms of fever. Subjects will also record symptoms and concomitant medications on the diary cards during the study.

^h Riamet[®] treatment will occur on Day 42±2, or earlier if there is failure of clearance or recrudescence of parasitaemia, or at the Investigator's discretion.

ⁱ Primacin[™] treatment if required (Section 6.1.5 of protocol).

^j ECG to be performed in triplicate at 4, 6, 8, 12, 24 and 72 h post-OZ439 and PQP dosing, or at the Investigator's discretion

^k At the time of admission to clinical unit only.

^l Only if vital signs are abnormal, or at the Investigator's discretion.

	
STATISTICAL ANALYSIS PLAN
	
QP17C19

		
Page 16 of 53

SECTION 3: INTERIM ANALYSES

There are no formal interim analyses planned for this study.

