Therefore, the dose group specific PRR (PRR_{48, D}) and corresponding 95% CI is estimated as shown in Equation (4) and (5), respectively:

$$PRR_{48,D} = 10^{-48 \times \bar{\beta}_1} \quad (4)$$

$$95\% \text{ CI: } 10^{-48 \times (\bar{\beta}_1 \pm 1.96 \times SE(\bar{\beta}_1))} \quad (5)$$

Comparison of dose group specific PRR_{48S}

To determine whether there are differences between dose group specific PRR_{48S}, an omnibus test for between dose group differences is used [10]. The test is used to assess whether there are differences in the weighted mean slope of the J doses, using the test statistic shown in Equation (6) at the 5% significance level,

$$Q_B = \sum_{j=1}^J w_j \cdot (\bar{\beta}_j - \bar{\beta}_{..})^2 \sim \chi_{J-1}^2 \quad j = 1, \dots, J \quad (6)$$

The weight for the j^{th} dose is denoted by $w_j = \sum_{i=1}^{s_j} w_{ij}$ for subject i with appropriate overall fit in dose j . The $\bar{\beta}_j$ is the weighted average slope for dose j as defined in Equation (7), and $\bar{\beta}_{..}$ is the weighted grand mean given by:

	STATISTICAL ANALYSIS PLAN	QP17C19
		Page 34 of 53

$$\bar{\beta}_{..} = \frac{\sum_{j=1}^J w_j \bar{\beta}_j}{\sum_{j=1}^J w_j} \quad (7)$$

Interim analyses of comparisons between dose-group specific PRR_{48S} will first be performed for all dose groups within each cohort. Final analyses will include the comparison between the dose groups 1D vs. 3A, each receiving the same dose combination (OZ439 400 mg, PQP 640 mg). Final analyses will be performed based on the factorial design of the study, for the following dose groups to assess differences in increasing PQP dose with constant 200 mg dose of OZ439 (1A vs. 1B vs. 2B), 400 mg dose of OZ439 (1C vs. 1D/3A) and 800 mg dose of OZ439 (2A vs. 3B). Similarly, comparisons will be made to assess differences between dose groups with increasing OZ439 dose with constant 480 mg dose of PQP (1A vs. 1C) and 640 mg dose of PQP (1B vs. 1D/3A vs. 3B). Type 1 error corrections will not be performed as analyses was implicit by the study design.

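### SAP 8.4 tests PRR48 between dose groups nine times at 5% without correction or an exploratory label; the chance of a false dose difference is about 20% over the five final dose contrasts and 26% over all eight

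*SAP*

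**What the plan says.** SAP 8.4 (Comparison of dose group specific PRR48s) assesses differences between weighted mean slopes "using the test statistic shown in Equation (6) at the 5% significance level". The test is used in two stages.

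- **Interim.** Comparisons "will first be performed for all dose groups within each cohort". With three cohorts this is three tests: 1A/1B/1C/1D, 2A vs 2B, and 3A vs 3B.
- **Final.** Six tests. The first is a same-dose check: "Final analyses will include the comparison between the dose groups 1D vs. 3A, each receiving the same dose combination". Three examine PQP dose at fixed OZ439 dose (1A vs 1B vs 2B; 1C vs 1D/3A; 2A vs 3B). Two examine OZ439 dose at fixed PQP dose (1A vs 1C; 1B vs 1D/3A vs 3B).

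On multiplicity, the SAP says "Type 1 error corrections will not be performed as analyses was implicit by the study design". It gives no order of testing, no deciding comparison and no exploratory label. A Scheffe method is specified, but only for the optional post-hoc pair-wise contrasts that follow.

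PRR is a secondary endpoint (SAP 2.3). The test results have their own planned table (14.2.5, SAP Appendix 2), and SAP 8.6 puts PD results in the main text of the study report.

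Protocol 10.3.3 plans a dose-specific PRR with its 95% CI and no test between doses. Protocol 10.1 adds: "This study is not powered to compare IMP doses, but rather to answer the primary objectives".

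**The concern.** The reason given for the waiver does not do what is asked of it. Listing comparisons in advance limits data-driven selection, but it leaves the error rate of the family unchanged. Nor were most of these comparisons fixed by the starting design. SAP 2.1 says the Cohort 2 and 3 doses were settled adaptively, and seven of the nine tests use a group from those cohorts; only the Cohort 1 omnibus test and 1A vs 1C do not.

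At stake is how the study report may describe dose effects on parasite clearance. With a 5% decision level, overlapping tests and no rule for reading them together, one isolated result below 0.05 could be presented as an established OZ439 or PQP dose effect. Tests of the same question in different strata, such as PQP dose at 200, 400 and 800 mg OZ439, could also disagree, and the SAP does not say which would stand.

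**Working it through.** The documents state no familywise error rate, so there is no plan figure to reproduce beyond the 5% level per test.

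**Inputs**
- Level per test: 0.05 (SAP 8.4).
- Group sizes (SAP 2.1): 2 each in 1A–1D; 4 each in 2A, 2B, 3A and 3B. Total 4×2 + 4×4 = 24.
- Statistic (SAP 8.4, equation 6): Q_B = Σ w_j (β̄_j − β̄..)², referred to chi-square with J − 1 degrees of freedom. The weight w_j is the sum of the subjects' 1/SE².
- Assumed, because the documents give no values: equal subject SEs, so w_j is proportional to group size; all 24 subjects evaluable; no true difference between any groups.
- Assumed, because the SAP does not say: 1D/3A is pooled (2 + 4 = 6 subjects).

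**Step 1: count.** Three interim tests plus six final tests make nine. 1D vs 3A compares identical doses, so a false positive there is a cohort difference and not a dose difference. That leaves 3 + 5 = 8 dose contrasts, five of them final.

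**Step 2: if the tests were independent.** The chance of at least one false positive is 1 − 0.95^k:
- k = 5: 22.6%
- k = 6: 26.5%
- k = 8: 33.7%
- k = 9: 37.0%

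**Step 3: allow for shared groups.** The tests overlap; 1A, for example, enters three of them. Q_B was therefore simulated for all nine tests under the null with 400,000 replicates. Each test alone rejected in 4.9% to 5.1% of replicates, as it should. The chance of at least one rejection was:

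| Set of tests | Base case | Unequal subject SEs | 1D and 3A kept separate |
|---|---|---|---|
| Five final dose contrasts | 19.6% | 19.5% | 19.3% |
| All eight dose contrasts | 25.8% | 25.5% | 25.2% |
| Six final tests, with 1D vs 3A | 23.7% | 23.5% | 21.2% |
| All nine tests | 28.8% | 28.4% | 26.8% |

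The expected number of false dose differences is 5 × 0.05 = 0.25 over the final dose contrasts and 8 × 0.05 = 0.40 over all eight.

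**Step 4: does each test hold 5%?** The weights use only each subject's own regression SE. If slopes also vary between subjects, with variance 0.5 to 2 times SE² (an assumed range; the documents give no value), the simulated rate rises to between 41% and 76% for the five final dose contrasts, and to between 50% and 84% for all eight. That is a separate matter from multiplicity. It means the Step 3 figures isolate multiplicity and are not an upper limit.

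**The case against.** The case on the other side is substantial. This is a small Phase 1b study with no formal power calculation (SAP 2.4). PRR48 is secondary, and the primary endpoints are the PK/PD relationship and safety. No success criterion or dose decision is tied to a PRR48 p-value: SAP 3.1 bases the choice of later doses on review of safety and PK/PD outcomes. Counting the within-cohort looks in the same family as the final tests is a choice. The percentages need a null across 200–800 mg OZ439 and 320–960 mg PQP; if some dose effects are real, fewer tests can give a false positive. All of this stands. It limits the importance of the point and argues for a label rather than a formal correction. It does not repair the reason given for the waiver.

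A reader might also infer more than the documents support:

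- **That 24% and 29% are the chances of a false dose difference.** They include 1D vs 3A, where the doses are the same. The figures for dose differences are 20% and 26%.
- **That the waiver contradicts the protocol.** Protocol 10.3.9 marks multiplicity as not applicable, which agrees with making no adjustment. Protocol 10.1 is a caveat on power; it neither forbids comparisons nor labels them exploratory. SAP 1.1 also lets the SAP supersede the protocol. The gap is that the SAP adds tests the protocol did not describe, without a rule for reading them.
- **That the interim comparisons breach SAP Section 3.** That section says "There are no formal interim analyses planned for this study", but the word formal matters: SAP 3.1 then allows additional interim analyses in support of decisions, using the methods described later in the SAP. The within-cohort comparisons can be read as that kind. SAP 8.4 simply does not say so.
- **That the pair-wise tests are uncontrolled as well.** The Scheffe method is specified for them. It does not reach the nine omnibus tests.

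**Conclusion.** The point holds as a modest, inexpensive improvement. If no dose affects PRR48, the plan gives about a 20% chance of at least one false dose difference over the five final dose contrasts and about 26% over all eight. With the same-dose check included, the chance of any false positive is about 24% over the six final tests and 29% over all nine. These figures rest on equal subject SEs, 24 evaluable subjects, pooled 1D/3A and tests that truly hold 5%. Unequal SEs, or keeping 1D and 3A separate, change the dose-contrast figures by less than one percentage point. The point does not bear on the primary endpoints, and the documents do not show that any dose was or would be chosen on these tests.

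**What to change.** In SAP 8.4:

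1. Delete the sentence that waives type 1 error correction, and the reference to the 5% significance level.
2. Label all PRR48 between-group comparisons exploratory: within-cohort, final and pair-wise. Carry the label into Table 14.2.5.
3. Report estimates with intervals and nominal p-values, and state that no single comparison supports a claim of a dose difference.
4. State that the within-cohort comparisons are informal interim analyses of the kind SAP 3.1 allows.

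This agrees with protocol 10.1 and costs only wording; no data or analyses change. The downside is that an isolated p < 0.05 can no longer be reported as an established dose effect.

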2.1 STUDY DESIGN AND TREATMENTS

This is a single-centre, open-label, adaptive, randomised study using the *P. falciparum* induced blood stage malaria (IBSM) inoculum as a model to characterise the safety, tolerability, PK, pharmacodynamic (PD) activity, and PK/PD relationship of combined single dose administration of OZ439 and PQP.

The study was conducted in three cohorts of 8 subjects each using up to 4 different single doses of OZ439 and PQP in each cohort. Subjects were malaria naïve healthy males or females, aged between 18-55 years old, who met all of the inclusion criteria and none of the exclusion criteria.

The first cohort was composed of 4 groups of 2 subjects each. Subjects were randomised into one of 4 dose groups and administered single oral doses of OZ439 and PQP in combination. The combined dose of OZ439 and PQP was different for each of the 4 groups in this cohort as shown in Table 1.

Table 1. OZ439 and PQP Cohort 1 dose groups

Drug	Dose group			
	1A	1B	1C	1D
OZ439 (mg)	200	200	400	400
PQP (mg)	480	640	480	640

The OZ439 and PQP dose levels and the number of subjects per dose for Cohorts 2 and 3 were determined adaptively during the study.

After review of the PK/PD and safety data from Cohort 1 by the Safety and Data Review Team (SDRT) it was determined that cohort 2 would be composed of 2 dose groups of 4 subjects each. Subjects were randomised into one of 2 dose groups and administered single oral doses of OZ439 and PQP in combination. The combined dose of OZ439 and PQP will be different for each dose group in this cohort as shown in Table 2.

Table 2. OZ439 and PQP Cohort 2 dose groups

Drug	Dose group	
	2A	2B
OZ439 (mg)	800	200
PQP (mg)	960	320

A similar analysis was done at the end of Cohort 2 by combining data from cohorts 1 and 2 to decide the doses to be tested in Cohort 3. Two groups of 4 subjects each were considered. Subjects were randomised into one of 2 dose groups and administered single oral doses of OZ439 and PQP in combination as shown in Table 3.

Table 3. OZ439 and PQP Cohort 3 dose groups

Drug	Dose group	
	3A	3B
OZ439 (mg)	400	800
PQP (mg)	640	640

Each subject was inoculated on Day 0 with approximately 2,800 viable parasites of *P. falciparum*-infected human erythrocytes administered intravenously. Subjects were followed up daily via phone call or text message on Days 1 to 3 post-inoculation to solicit any AEs.

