Post-hoc pair-wise comparisons can be calculated using the test statistic $Z_G = \frac{G}{\sqrt{v_G}}$, where G is the contrast ($G = c_1 \bar{\beta}_1 + \dots + c_j \bar{\beta}_j$) and v_G is the variance of the contrast ($v_G = \frac{c_1^2}{w_1} + \dots + \frac{c_j^2}{w_j}$). The p-value of the L pair-wise comparisons will be calculated using the Scheffe method, by comparing Z_G^2 to a chi-squared distribution with $L - 1$ degrees of freedom.

Recrudescence

Recrudescence will be defined as subjects who show substantial increases in parasitaemia after the initial clearance and are treated with a standard course of Riamet® prior to the compulsory scheduled timepoint for Riamet® treatment.

PD Parameters Analysis

All PD parameters will be listed. Summary statistics will be produced by dose group. For continuous data, the number of observations, mean, SD, median, minimum and maximum values will be reported. The number and percentage of subjects will be reported for incidence data.

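### The Scheffe post-hoc p-values for PRR48 take their degrees of freedom from the number of pairs tested instead of the number of dose groups, which matters for the four-group Cohort 1 comparison

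*SAP*

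**What the plan says.** SAP 8.4, under the comparison of dose-group PRR48 values, gives an omnibus statistic Q_B (equation 6). It compares the weighted mean slopes of J doses, refers Q_B to a chi-squared with J − 1 degrees of freedom, and tests "at the 5% significance level". These comparisons "will first be performed for all dose groups within each cohort", which the SAP labels interim. A list of final comparisons along the rows and columns of the dose grid follows. That paragraph ends by saying that type 1 error is not corrected.

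The next paragraph adds an optional step: "Post-hoc pair-wise comparisons can be calculated using the test statistic" Z_G = G/√v_G, where G is a contrast of the weighted slopes and v_G its variance. It continues that p-values for the L "pair-wise comparisons will be calculated using the Scheffe method, by comparing" the square of Z_G "to a chi-squared distribution with $L - 1$ degrees of freedom". L is thus a count of comparisons, a different symbol from the J used for dose groups.

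**The concern.** Scheffe's method protects all contrasts among a set of means at once. Its reference distribution depends on how many means there are, not on how many contrasts the analyst chooses to look at. Under the rule as written, the p-value for one and the same contrast changes with the number of other pairs run alongside it. The SAP does not fix that number.

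The error has no constant direction. With many pairs the rule is stricter than Scheffe, with few pairs it is more lenient, and with one pair it has no degrees of freedom. A post-hoc p-value labelled Scheffe in the study report would not be one, except where L happens to equal J.

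**Working it through.** **Inputs.** The 5% level, Q_B on J − 1 degrees of freedom, the definitions of G, v_G and L, and the list of comparisons are all in SAP 8.4. Group numbers come from SAP 2.1: "The first cohort was composed of 4 groups of 2 subjects each", and Cohorts 2 and 3 have two groups each. I assume that the 5% level stated for the omnibus test also applies to the pairs, and that 1D/3A in the list means those two groups pooled.

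**Step 1: the Scheffe reference from equation (6).** Let b_j be the weighted slope of dose group j, b its weighted grand mean and w_j its weight. For a contrast with Σc_j = 0, G = Σc_j b_j = Σc_j(b_j − b). By the Cauchy-Schwarz inequality, G² ≤ (Σc_j²/w_j) × (Σw_j(b_j − b)²) = v_G × Q_B. Hence Z² = G²/v_G ≤ Q_B, with equality when c_j is proportional to w_j(b_j − b). The largest Z² over all contrasts is therefore Q_B, and its reference is the chi-squared on J − 1 degrees of freedom.

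A numerical check uses arbitrary slopes 0.03, 0.05, 0.04, 0.07 and weights 40,000, 90,000, 30,000, 50,000. Q_B and the largest Z² are both 38.952.

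**Step 2: apply both rules to the planned sets.** With all pairs tested, L = J(J − 1)/2.

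| Planned set | J | L | SAP df (L − 1) | Scheffe df (J − 1) | 5% critical Z², SAP | 5% critical Z², Scheffe |
|---|---|---|---|---|---|---|
| Cohort 1: 1A, 1B, 1C, 1D | 4 | 6 | 5 | 3 | 11.07 | 7.81 |
| 1A, 1B, 2B; and 1B, 1D/3A, 3B | 3 | 3 | 2 | 2 | 5.99 | 5.99 |
| 1D vs 3A; 1C vs 1D/3A; 2A vs 3B; 1A vs 1C; Cohort 2; Cohort 3 | 2 | 1 | 0 | 1 | none | 3.84 |

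**Step 3: four groups, all six pairs.** On the scale of |Z| the threshold is √11.07 = 3.33 instead of √7.81 = 2.80 (rounded from 2.795). Tail probabilities:

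| Z² | p as written (5 df) | p by Scheffe (3 df) |
|---|---|---|
| 8.0 | 0.156 | 0.046 |
| 8.5 | 0.131 | 0.037 |
| 9.0 | 0.109 | 0.029 |
| 10.0 | 0.075 | 0.019 |

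In 1,000,000 simulated null data sets with equal weights, the chance of at least one significant pair among the six was 0.5% under the rule as written and 2.7% under J − 1.

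**Step 4: two groups.** With slopes 0.03 and 0.05 and weights 40,000 and 90,000, Z² = 0.02²/(1/40,000 + 1/90,000) = 11.077, and Q_B is also 11.077. The omnibus test on 1 degree of freedom is the pair-wise test. If the post-hoc rule were applied as well, it would have 0 degrees of freedom. R, one of the packages named in SAP 8.5, then returns p = 0 for any positive Z², and Python returns no value.

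**Step 5: fewer pairs than groups.** When L < J, L − 1 < J − 1 and the threshold falls below Scheffe's. Two pairs give 1 degree of freedom and a critical value of 3.84, which is no adjustment. For two pairs sharing a group, the simulated chance of at least one false positive was 9.1%. When L equals J, for example four of the six Cohort 1 pairs, the two rules agree by coincidence.

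**The case against.** The strongest reply is that little depends on this line. Every final comparison has two or three groups. The three-group sets are correct as written when all three pairs are tested, and the two-group sets need no post-hoc step. The one four-group set is an interim comparison with two subjects per group. The post-hoc tests are optional, and SAP Appendix 2 lists a table for the Q_B test (Table 14.2.5) but none for pairs. PRR is a secondary endpoint (SAP 2.3), and protocol 10.1 says that the study is not powered to compare doses. All of this stands and limits the impact. It does not make the formula right, and nothing elsewhere in the documents corrects it.

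A reader might infer more than the documents support:

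- That the error makes the post-hoc tests contradict the omnibus test. A significant Q_B with no significant pair can also occur under correct Scheffe, because the contrast that attains Q_B need not be a pair.
- That real dose differences will be missed. The 5% decision for Cohort 1 changes only when Z² lies between 7.81 and 11.07, and the documents give no effect size from which to judge how likely that is.
- That dose selection was affected. SAP 3.1 bases it on safety, tolerability and PK/PD outcomes; no dose decision is tied to these p-values.
- That the SAP plans to test only two of three pairs. It does not; Step 5 only shows what the rule would do.

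**Conclusion.** The point holds as an error in one formula with narrow reach. The reference for the Scheffe pair-wise tests should have J − 1 degrees of freedom. Among the planned sets, the material effect is on the Cohort 1 within-cohort comparison, where testing all six pairs makes the rule too strict by two degrees of freedom.

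This rests on three assumptions: all six Cohort 1 pairs are tested, the 5% level applies to the pairs, and 1D and 3A are pooled where the SAP writes them together. If 1D and 3A were kept apart, the 640 mg PQP set would also have four groups, with the same consequence. The conclusion follows from the algebra of equation (6) and does not depend on the reference the SAP cites for that test.

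**What to change.** In SAP 8.4:

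1. Replace L − 1 degrees of freedom with J − 1 degrees of freedom, where J is the number of dose groups in the corresponding omnibus test.
2. State that for two groups the omnibus test is the pair-wise test and no post-hoc step is run.
3. Reconcile the Scheffe adjustment with the preceding statement that type 1 error is not corrected, for example by limiting that statement to the planned omnibus comparisons.

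The cost is a few lines of SAP text and one argument in the code. No data collection or design feature changes.
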